10.4 ADVERSE EVENT REPORTING

The adverse events that an IRB/EC considers reportable are dependent on the particular IRB/EC. To avoid underreporting, BIOTRONIK recommends that, at a minimum, the investigator reports the procedure-related, lead-related, and pulse generator-related adverse events that occur during the Protego Post-Approval Registry to BIOTRONIK and the IRB/EC.

The registry site will report the adverse event on the Adverse Event eCRF. Additionally, registry sites may report adverse events through MedWatch, FDA's adverse event reporting tool for market-released devices. As defined in BIOTRONIK's internal procedures, these adverse events may be reported by BIOTRONIK through manufacturer's MedWatch reports.

11. IRB APPROVAL

Institutional Review Board (IRB) approval is required from each institution prior to participation in this post-approval registry. Subject enrollment may not begin until the IRB and BIOTRONIK have granted approval for the investigational site. IRB approval is also required throughout the duration of this clinical investigation. If IRB approval is withdrawn, BIOTRONIK must be notified within 5 working days.

11.1 OTHER INSTITUTIONS AND PHYSICIANS

This post-approval registry is not transferable to other institutions attended by the investigator unless prior approval is obtained from both BIOTRONIK and the appropriate IRB/EC. Additional investigational sites may be included in this registry. However, there are certain situations where an investigator might not be immediately available to provide the necessary medical care for a subject with a registry device (e.g. when a subject goes to the emergency room for medical treatment). In any such situations, the IRB/EC and the investigator must continue to provide oversight for that subject's medical care and rights as a research subject. BIOTRONIK will ensure that the necessary support personnel are available to any physician providing immediate care for a subject in order to answer questions about the device and provide guidance in collecting the necessary documentation required for the clinical registry.

12. INFORMED CONSENT

Prior to the subject's participation in the investigation, informed consent is required from all subjects. Informed consent should be obtained in accordance with the FDA regulations (21CFR, Part 50). The investigator is required to inform BIOTRONIK and the reviewing IRB/EC within 5 days if any subject was not appropriately consented to participate in the registry. BIOTRONIK is then required to report any failure to obtain subject consent to the FDA within 5 working days of learning of such an event. In order to assist with the consent process, BIOTRONIK will provide a template subject consent form to investigational sites participating in the registry.

13. RECORDS AND REPORTS

13.1 INVESTIGATOR RECORDS

Investigators are required to maintain on file the following accurate, complete and current records relating to this investigation:

- All correspondence relating to the registry with another investigator, an IRB/EC, BIOTRONIK, a monitor, or the FDA, or any other regulatory authority. (e.g., a letter sent from the investigator to the IRB/EC).
- A copy of the registry protocol
- Signed investigator or research agreement
- Signed Financial Disclosure Form
- A copy of the IRB/EC letter approving the research registry
- A copy of the IRB/EC approved subject Informed Consent Form
- All clinical forms and documentation, including:
 - o a copy of the signed subject consent form
 - o all supporting documentation for data entered into the EDC system
 - o records of any adverse device effect, including supporting documentation
 - o records pertaining to subject deaths during the investigation
 - o documentation and rationale for any deviations from the clinical protocol
 - o any other records required by BIOTRONIK

13.2 INVESTIGATOR REPORTS

Investigators are required to prepare and submit to BIOTRONIK the following complete, accurate, and timely reports on this registry when necessary:

- Notification of a subject death during the investigation
- Notification of the withdrawal of IRB/EC approval
- Annual progress reports prepared for the IRB/EC
- Notification of any deviations from the investigational plan
- Notification that an informed consent was not obtained from the subject

- Final summary report prepared for the IRB/EC
- Any other information upon the request of an IRB/EC, FDA, or BIOTRONIK

Table 5 outlines the responsibilities, including time constraints, for submitting the above reports.

Table 5: Investigator Reporting Responsibilities

Type of Report	Report to BIOTRONIK	Report to IRB/EC	Time Constraints of Notification
Subject Death During Investigation	Required	Required	BIOTRONIK as soon as possible and as required by reviewing IRB/EC
Adverse Event	Required	IRB/EC dependent	Within 10 calendar days after notification of the event
Unanticipated Adverse Device Effect	Required	Required	Within 10 working days after notification of the effect
Subject Withdrawal	Required		Within 5 working days
Withdrawal of IRB/EC Approval	Required		Within 5 working days
Progress Report	Required	Required	Submitted not less often than yearly
Significant Deviations from Investigational Plan	Required	Required	Within 5 working days after emergency to protect life or physical well-being of subject, otherwise prior approval by BIOTRONIK is required
Informed Consent Not Obtained	Required	Required	As soon as possible after discovery

13.3 SPONSOR RECORDS

BIOTRONIK will maintain the following records:

- All correspondence that pertains to the registry with the investigator(s), IRB/EC, and FDA
- Investigator agreements, financial disclosures, and current curriculum vitae
- Name and address of each investigator and each IRB/EC that is involved with the investigation
- Adverse events and complaints
- Adverse device effects (whether anticipated or unanticipated)
- Electronic case report form data
- Completed subject informed consent forms
- Clinical investigation plan and report of prior investigations

- Screening visit reports
- Monitoring reports
- Clinical progress reports
- Statement of the extent to which the good manufacturing practice regulation is part 21CFR820 will be followed in manufacturing the device

13.4 SPONSOR REPORTS

Table 6: Sponsor Reporting Responsibilities

Type of Report	Prepared by BIOTRONIK for	Time Constraints of Notification
Withdrawal of IRB/EC Approval	FDA, all reviewing IRBs/ECs and participating investigators	Within 5 working days of receipt of notice of withdrawal of approval
Withdrawal of FDA Approval	Reviewing IRBs and participating investigators	Notification will be made within 5 working days.
Progress Report	FDA, all reviewing IRBs/ECs	A progress report will be submitted at least annually
Recall and Disposition	FDA, all reviewing IRBs/ECs	Notification will be made within 30 working days and will include the reasons for any request that an investigator return, repair or otherwise dispose of any devices.
Final Report	FDA, all reviewing IRBs/ECs and participating investigators	Notify FDA within 30 working days of the completion or termination of the investigation. A final report will be submitted within 6 months after completion or termination of the registry.

APPENDIX A: DEFINITION OF TERMS

AE (Adverse Event) – An unwanted affect detected in participants either implant procedure-related, pulse generator-related, lead-related, or other. The term is used whether or not the effect can be attributed to the leads in the study. For the purposes of this study, the CEC will indicate whether the adverse event relatedness to the Protego lead is: not related, related, possibly related, or unknown.

ACC/AHA – American College of Cardiology/American Heart Association

Cardiac Perforation – Penetration of the lead tip through the myocardium (including microperforation), either clinically suspected or confirmed by chest x-ray, fluoroscopy, echocardiogram, intracardiac electrogram and/or visually.

CEC – Clinical Events Committee

Clinical Failure – Inability of the lead to correctly sense or pace in the heart, not attributable to a mechanical malfunction of the lead or pulse generator that remains unresolved despite reprogramming and/or repositioning.

CFR – Code of Federal Regulations

Conductor Fracture – See Lead Fracture

Confirmed Failure – A lead having clinically relevant characteristics that are outside the performance limits established by BIOTRONIK while implanted and in service, as confirmed by analysis, except for changes in characteristics that are due to induced malfunctions. Lead damage caused during or after explant is not considered a failure.

Chronic Threshold – Chronic threshold is defined as the pacing threshold determined at the subject's 3 month follow-up visit.

eCRF – Electronic Case Report Form

EDC – Electronic Data Capture system

Exit Block – The failure of an intact pacing system to capture the heart because the stimulation threshold exceeds the output of the pacemaker.

Explantation – Surgical removal of a lead during the acute implant stage, whereby the lead has not been chronically implanted and can be easily removed by simple traction.

Extracardiac Stimulation – Clinical observation of inadvertent nerve/muscle stimulation other than cardiac muscle, such as the diaphragm or pectoral muscles.

Extraction of a Lead – Surgical removal of a chronically implanted lead.

Failure to Capture or Loss of Capture – Intermittent or complete failure to achieve cardiac stimulation at programmed output delivered outside of the cardiac refractory period.

High Pacing Threshold – One of the following definitions must be met:

1. At implant, thresholds for the Protego lead that are greater than 3.0 V at 0.4 ms or 0.5 ms, or
2. At follow-up, pacing thresholds for the Protego lead that have increased two fold from the chronic threshold value, and are greater than 3.5V at 0.4 ms or 0.5 ms.

Insulation Breach/Break – Visual, electrical, or radiographic evidence of a disruption or break in the insulation of a lead.

Intermittent Capture – Ineffective and inconsistent cardiac stimulation at irregular intervals in response to cardiac pacing delivered outside of the cardiac refractory period with a pacing output that exceeds the safety margin (which is twice the measured pacing threshold).

IRB – Institutional Review Board

Lead Dislodgment or Lead Migration – Radiographic, electrical or electrocardiographic evidence of electrode displacement from the original implant site or electrode displacement that adversely affects pacing, and/or lead performance.

Lead Fracture – Visual, electrical and/or radiographic evidence of mechanical break within the lead conductor (connectors, coils and/or electrodes).

Lead Impedance Out of Range – Pacing impedance is considered abnormal if a measurement is ≤ 200 ohms or ≥ 2000 ohms. Shock impedance is considered abnormal if a measurement is ≤ 20 ohms or ≥ 150 ohms.

Loss of Sensing – Complete failure to sense any intrinsic events that occur outside the programmed refractory periods at programmed sensitivity settings.

LV lead – Left ventricular lead

Non-healing Pocket Dehiscence – Separation of wound edges around the pocket of the implanted pulse generator that have not healed.

Oversensing – Misinterpretation of cardiac or non-cardiac events as cardiac depolarization, such as T-waves, skeletal muscle potentials, and extracardiac electromagnetic interference (EMI).

Pneumothorax – Air or fluid in the pleural space surrounding the lung leading to collapse or partial collapse of the lung.

Premature Battery Depletion – Reaching Elective Replacement Indicator (ERI) before the predicted date.

Mechanical Failure – Malfunction of the lead through a break in the conductor, insulation or connector pin leading to loss of pacing/sensing.

RA lead – Right atrial lead

Skin Erosion – Deterioration of tissue over an implanted device or the movement of a lead toward or through the skin.

Suspected Generator Failure – Pulse generator issue that is potentially an electrical malfunction.

Suspected Lead Failure – Lead issue that is potentially a mechanical or electrical malfunction.

Tamponade – Compression of the heart caused by blood accumulation in the space between the myocardium and the pericardium.

Thrombosis – The development of a blood clot in a vein or artery.

Twiddler's Syndrome – A condition where the pulse generator leads are dislodged by the subject unwittingly rotating the subcutaneous pulse generator.

Undersensing – Intermittent failure to sense any intrinsic events that occur outside the programmed refractory period.

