2.1.1 Primary Endpoint 1: Protego DF4 Lead Safety – 5-Year Adverse Event-Free Rate

The purpose of primary endpoint 1 is to evaluate the overall incidence of adverse events related to the Protego DF4 lead or header (as defined in Section 10) from implant through 5 years. Assuming that the expected Protego DF4 lead or header-related adverse event rate at 5 year post-implant (proportion of subjects with at least one AE in the timeframe from implant through 5 year post-implant) is 7.5% or less, then the primary safety endpoint will be evaluated in the following testable hypothesis in superiority format.

H₀: The adverse event-free rate (AEFR) for subjects receiving the Protego DF4 lead at 5 years post-implant is less than or equal to 92.5%

$$\text{AEFR} \leq 92.5\%$$

H_a: The adverse event-free rate (AEFR) for subjects receiving the Protego DF4 lead at 5 year post-implant is greater than 92.5%

$$\text{AEFR} > 92.5\%$$

A rejection of the null hypothesis would demonstrate that the adverse event-free rate is greater than 92.5%.

2.1.2 Primary Endpoint 2: Protego DF4 Lead Safety – Individual 5-Year Adverse Event-Free Rates

Each of the individual types of adverse events contributing to primary endpoint 1 will be evaluated separately in the following superiority hypothesis.

H₀: The individual adverse event rate (AEIndividual) for a given type of AE for the Protego DF4 lead at 5 years post-implant is greater than or equal to 1%

$$\text{AEIndividual} \geq 1\%$$

H_a: The individual adverse event rate (AEIndividual) for a given type of AE for the Protego DF4 lead at 5 years post-implant is less than 1%

$$\text{AEIndividual} < 1\%$$

If the two-sided, 95% upper confidence bound is no more than 1% for individual adverse events, then the null hypothesis will be rejected for that AE type.

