6. RISKS AND RISK MINIMALIZATION

All devices included in this registry are legally marketed and being prescribed by physicians according to FDA approved indications for use.

As with any implantable device, there are always potential risks that accompany the device. The following list provides the potential risks that may occur with the Protego DF4 lead in combination with an ICD or CRT-D device.

- Acceleration of arrhythmias
- Air embolism
- Allergic reactions to contrast media
- Arrhythmias
- Bleeding
- Body rejection phenomena
- Cardiac tamponade
- Chronic nerve damage
- Damage to heart valves
- Damage to lead during implant procedure
- Device migration
- Elevated pacing thresholds
- Embolism
- Erosion or pocket erosion
- Extrusion
- Fluid accumulation
- Hematomas, cysts, or fibrotic tissue
- Incomplete lead connection with the pulse generator
- Infection
- Inappropriate detection of ventricular arrhythmias
- Inappropriate therapy, including inappropriate shocks
- Keloid formation
- Lead abrasion and discontinuity
- Lead migration / dislodgment
- Lead fracture / insulation damage
- Lead perforation
- Lead-related thrombosis

-
- Local tissue reaction / fibrotic tissue formation
 - Muscle or nerve stimulation
 - Myocardial damage
 - Myopotential sensing
 - Pacemaker mediated tachycardia
 - Pneumothorax
 - Potential death due to inability to defibrillate or pace
 - Psychological effects (dependency, depression, fear of premature battery depletion, fear of shocking while awake, fear that shocking ability may be lost, anxiety about device resulting from frequent shocks, imagined (phantom) shock)
 - Random component failure
 - Shunting current or insulating myocardium during defibrillation with internal or external paddles
 - Thromboembolism
 - Undersensing of intrinsic signals
 - Valvular damage
 - Venous occlusion
 - Venous or cardiac perforation
 - Ventricular ectopy

These risks can be minimized through use of strict aseptic technique, compliance with the registry protocol and technical implant procedures, adherence to the guidelines for selection of subjects, close monitoring of the subject's physiologic status during the implant and follow-up procedures, and by promptly supplying BIOTRONIK with all pertinent information required by this protocol.

BIOTRONIK foresees no additional risks associated with this registry beyond those stated in the labeling for the respective pulse generators and leads.

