10.1.2 Pulse Generator-Related Adverse Events

An AE will be classified as pulse generator-related if any one of the following occurred:

- DF4 header connector malfunction
- DF4 header fluid intrusion
- Device migration
- Premature battery depletion
- Pulse generator failure
- Skin erosion

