10.1.3 Lead-Related Adverse Events

An AE will be classified as lead-related if any one of the following occurred:

- Cardiac perforation
- Diaphragmatic/extracardiac stimulation
- High pacing threshold³
- Intermittent capture / no lead capture
- Lead conductor fracture
- Lead dislodgement
- Lead impedance out of range, high impedance⁴
- Lead impedance out of range, low impedance⁴
- Lead failure
- Lead oversensing not due to external noise
- Lead oversensing due to external noise
- Lead-related thrombosis
- Lead-related infection
- Lead undersensing or loss of sensing
- Other unexpected complications that are identified through imaging and considered related to the ICD lead or DF4 connector

³ High pacing threshold is defined as:

A. At implant, threshold that is greater than 3.0V at 0.4ms or 0.5ms, OR

B. At follow-up, threshold that has increased two fold from the chronic (3 month follow-up) threshold value and is greater than 3.5V at 0.4ms or 0.5ms.

⁴ Lead impedance out of range is defined as a pacing impedance measurement of ≤ 200 Ohms or ≥ 2000 Ohms or a shock impedance measurement of ≤ 20 Ohms or ≥ 150 Ohms.

For each of these lead-related AEs, indicate:

- Confirmed lead integrity failure
- Suspected lead integrity failure
- No lead integrity failure

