10.3 ADVERSE EVENTS FOR THE ANALYSIS OF THE PRIMARY AND SECONDARY ENDPOINTS

10.3.1 Adverse Events for the Analysis of Primary Endpoints 1 and 2

If any of the following invasive actions occur in order to resolve an above listed Protego lead-related AE, the AE will be included in the primary safety endpoint analysis:

- Lead surgically repositioned
- Lead surgically explanted
- Lead surgically replaced
- Lead surgically abandoned
- Other lead-related surgery performed

Additionally, if any of the following non-invasive actions occur in order to resolve an above listed Protego lead-related AE, the Protego lead-related AE will be included in the primary endpoint analysis:

- Lead pacing polarity or pacing mode reprogrammed due to suspected lead failure.
- Lead abandoned and pacing disabled due to clinical failure or suspected lead failure
- Lead use continued based on medical judgment despite a known clinical failure or suspected lead failure

AEs that are corrected by reprogramming the pulse generator (other than the above) and resolved without invasive action will not be considered an adverse event counted towards the primary endpoints. For example, electrical reprogramming of the pacing polarity to eliminate extra-cardiac stimulation will not be considered an adverse event. Similarly, increasing pacing output as a result of an elevated threshold without further intervention does not count toward the primary endpoint analysis.

Subject deaths as a result of a Protego lead-related AE will be included in the primary endpoint analysis.

Primary endpoints 1 and 2 will exclude 1) lead dislodgements that occur within 30 days after lead implant or a lead revision procedure and 2) high pacing threshold, intermittent capture, no lead capture within 30 days after lead implant or a lead revision procedure. However, these will count towards the adverse event secondary endpoint.

In addition, the following two pulse generator-related adverse events will be included in the analysis of primary endpoints 1 and 2: DF4 header connector malfunction and DF4 header fluid intrusion.

10.3.2 Adverse Events for the Analysis of Secondary Endpoint 3

If any of the following invasive actions occur in order to resolve an above listed RA or LV lead-related AE, the AE will be included in the secondary endpoint analysis:

- Lead surgically repositioned
- Lead surgically explanted
- Lead surgically replaced
- Lead surgically abandoned
- Other lead-related surgery performed

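### Erosion of the Protego lead through the skin is classed by default as a pulse generator event, so lead surgery for it does not count in primary endpoints 1 and 2 unless it is reclassified or also filed as a lead event

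*Combined protocol and SAP*

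**What the plan says.** - **Definition.** Appendix A gives skin erosion two limbs. The first is breakdown of tissue over the device; the second is "the movement of a lead toward or through the skin".
- **Generator list.** Section 10.1.2 opens with "An AE will be classified as pulse generator-related if any one of the following occurred" and includes skin erosion, without separating the two limbs.
- **Lead list.** Section 10.1.3 has no erosion item. Its only open-ended entry is "Other unexpected complications that are identified through imaging and considered related to the ICD lead or DF4 connector". Section 6 names "Erosion or pocket erosion" among the known risks.
- **Entry to the primary endpoints.** The surgical route in 10.3.1 begins "If any of the following invasive actions occur in order to resolve an above listed Protego lead-related AE". From the generator list, 10.3.1 says that "the following two pulse generator-related adverse events will be included in the analysis of primary endpoints 1 and 2". Both of these concern the header: a malfunctioning connector and entry of fluid.
- **Everything else.** Section 10.3.2 sends other generator-related events that need invasive intervention to secondary endpoint 3. Section 2.1.3 attaches no hypothesis test to that endpoint.
- **Purpose.** Section 2.1.1 says that endpoint 1 is to "evaluate the overall incidence of adverse events related to the Protego DF4 lead or header", as Section 10 defines such events.
- **Adjudication.** Section 10.1 describes the lists as general classes for site reporting and allows the CEC charter to use others. Sections 4.2 and 10.2 give the CEC the final say on class and category, and on relatedness to the Protego lead.

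**The concern.** Two subjects have the same operation at 18 months: the Protego lead is surgically explanted. In one the lead had dislodged, in the other it had moved through the skin. By the written lists the first is a primary endpoint event and the second is a generator event outside both primary endpoints.

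Endpoint 1 tests the overall lead-or-header event-free rate against 92.5%, and endpoint 2 tests each contributing event type against 1%. If lead erosion is left out, endpoint 1 omits a lead complication that ended in lead surgery, and endpoint 2 never tests lead erosion as a type. Section 10.2 applies the same counting rules to the Kaplan-Meier analyses, so those would not show it either. The omission can only make the lead look better.

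**Working it through.** **1. Where the written rules send the event.** Take a Protego lead that moves through the skin and is surgically explanted, with no infection reported.

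- Appendix A: it meets the second limb of skin erosion.
- 10.1.2: skin erosion is generator-related.
- 10.1.3: no listed item fits well. The open-ended entry requires a complication that is unexpected and found by imaging, whereas erosion is a listed risk and is normally seen at the skin. Dislodgement is defined in Appendix A by displacement of the electrode.
- 10.3.1: it is neither a listed Protego lead-related event nor one of the two header events.
- 10.3.2: it needed invasive intervention, so it enters secondary endpoint 3.

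**2. What then happens to the subject in the 5-year test.** Section 2.4.3 keeps only subjects who reach 5 years or had an adverse event before then.

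- Lead explanted or capped with no new Protego lead: the subject is withdrawn (3.2.5.2, 3.3.3) and, having no primary event, drops out of the test.
- Lead kept, or replaced by another Protego lead, and 5 years completed: the subject counts as event-free.

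**3. The plan's own figures (Section 2.3).** With X the number of subjects with an event, endpoint 1 passes if X ≤ c, where c is the largest count with P(X ≤ c | n, 0.075) ≤ 0.025.

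- n = 750: c = 42, type I error 0.0247, power at a 5% event rate 80.1%. The stated 750 and 80% are reproduced.
- Attrition: 750/0.9^5 = 1270.1 (stated 1271) and 1000/0.9^5 = 1693.5 (stated 1694).

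None of these depends on how erosion is classified.

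**4. Illustration for endpoint 1.** I use n = 1000, the evaluable number for endpoint 2, which sets enrolment. Here c = 58: P(X ≤ 58) = 0.0208 and P(X ≤ 59) = 0.0282 at an event rate of 7.5%. Let e be the share of subjects whose only qualifying event is lead erosion. The documents do not give e; 0.1% to 0.5% is assumed. Take a lead whose true event rate, erosion included, is 7.5%.

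- Counted event-free: the counted rate is 0.075 − e.
- Dropped: n becomes 1000(1 − e) and the rate (0.075 − e)/(1 − e). The critical count stays at 58.

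| e (assumed) | Counted rate | P(pass), counted event-free | n and rate if dropped | P(pass), dropped |
|---|---|---|---|---|
| 0 | 7.5% | 2.1% | 1000, 7.50% | 2.1% |
| 0.1% | 7.4% | 2.7% | 999, 7.41% | 2.7% |
| 0.3% | 7.2% | 4.6% | 997, 7.22% | 4.6% |
| 0.5% | 7.0% | 7.4% | 995, 7.04% | 7.4% |

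The two routes give the same answer to the precision shown.

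**5. Illustration for endpoint 2.** The exact two-sided 95% upper bound for x events in n is the 0.975 quantile of Beta(x + 1, n − x). At n = 1000, 3 events give 0.87% (pass) and 4 give 1.02% (fail). Lead erosion would be judged by that rule if it were a listed lead type; at present it is not tested.

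**6. Power if lead erosion is counted.** Adding e to the planned 5% event rate, endpoint 1 power is P(X ≤ c | n, 0.05 + e):

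| e (assumed) | n = 750 | n = 1000 |
|---|---|---|
| 0 | 80.1% | 88.9% |
| 0.1% | 76.4% | 85.9% |
| 0.3% | 68.0% | 78.4% |
| 0.5% | 58.8% | 69.2% |

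**The case against.** **The lists are not the last word.** They serve site reporting, and the primary rates rest on CEC adjudication. A reader might infer that lead erosion is barred outright from the primary endpoints. The documents do not support that: the CEC can reclassify it, and an erosion also filed as lead-related infection and treated by lead surgery already counts. This stands, so exclusion is a default and not a certainty. It does not close the gap, because the protocol only permits alternative classes in the charter and gives no rule for lead erosion. Erosion without infection has no other clear route.

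**Such subjects are not all scored as successes.** That is another tempting inference, and it is wrong for the plain explant case, where the subject is withdrawn and leaves the test. The direction and, as the working shows, the size are the same either way.

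**Endpoint 1 promises no more than Section 10 defines.** Correct: Section 2.1.1 ties it to those definitions. The point is therefore that the definitions place a lead event under the generator, not that the endpoint breaks a wider promise.

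**The size is unsupported.** This also stands. Table 1 shows no erosion row among 1,999 subjects with the predecessor leads, although such events may have been classed elsewhere. Late dislodgement and suspected conductor fracture are each at 0.25% there, so 0.5% for erosion alone, with no other lead event filed, would be high. It would be wrong to read 7.4% as the plan's actual type I error.

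**The events remain visible.** They appear in secondary endpoint 3 with exact confidence intervals, and extractions are recorded (2.1.4). True, but neither is set against 92.5% or 1%.

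**Conclusion.** The point holds as a gap in event classification. By default, a Protego lead erosion treated by lead surgery is reported in secondary endpoint 3 and left out of both primary endpoints, unless the CEC reclassifies it or another listed lead event is filed with it. The omission favours the lead whether the subject is dropped or counted event-free.

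Its size cannot be derived from the documents. Under an assumed 0.1% to 0.5% of subjects affected, at n = 1000 and a true event-free rate of 92.5%, the chance of passing endpoint 1 rises from 2.1% to between 2.7% and 7.4%. The effect is likely at the low end or smaller, because erosion filed together with a lead infection already counts and the CEC may correct some of the rest. The plan's sample size figures are unaffected. The gap should be closed because it touches the content of the primary endpoints and the change is small.

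**What to change.** - **Appendix A:** split the term into erosion of tissue over the pulse generator, and lead erosion (movement of a lead toward or through the skin).
- **10.1.2:** keep only erosion over the pulse generator.
- **10.1.3:** add lead erosion, so that Protego lead erosion adjudicated by the CEC as related, and meeting one of the actions in 10.3.1, counts in endpoints 1 and 2. Right atrial and left ventricular lead erosion would follow the existing rules in 10.3.2.
- **Adverse event eCRF and CEC charter:** use the same split.

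The cost is the wording, one more choice on the form, and a slightly less favourable event-free rate. Endpoint 1 also loses some power, by an amount that depends on the unknown erosion rate: at n = 1000, from 88.9% to 85.9% if erosion adds 0.1% to the planned 5% event rate, or to 69.2% if it adds 0.5%. Recheck the power of endpoint 1 when the change is made, with the assumed erosion rate stated.
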